### 10.2.2 CPC 3-5 at 180 Days

The %patients with CPC 3-5 at Day 180 will be analysed using the same methodology as used for the analysis of the CPC scores at discharge (see section 10.2.1) whereby all patients who did not have CPC scores due to death are given a score of 5.

A sensitivity analysis will be performed whereby all patients who did not die and do not have CPC data will be given a score of 5.

### 10.2.3 SF-36 Questionnaire at Day 180

Of main interest is the total score obtained from the SF-36 questionnaire. In addition, the subscales will be analysed using the same methodology.

It should be kept in mind that a considerable proportion of patients will have died prior to Day 180 and that therefore, the SF-36 results in these patients are not defined. A comparison of the scores in the survivors will yield biased estimates of the treatment effect, since the element of randomisation is lost in such comparison if survival depends on the assigned treatment group.

Therefore, the effect of randomised group will be evaluated by the "survivor average causal effect" (SACE), defined as the effect of randomised treatment on the outcome among the subgroup of patients that would have survived under either treatment arm. The SACE will be calculated as explained by Hayden et al by weighing the result of each survivor by the estimated survival probability in the other group. The confidence interval will be obtained by bootstrapping (500 samples).

The estimated survival probabilities will be obtained from a logistic regression using survival as dependent variable and the baseline covariates given in Section 7.4 as independent variables.

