### **7.3 Statistical Comparisons between Groups**

Since randomization was stratified by the presence of shockable rhythm, all comparisons between groups should account for this stratification.

So, an ANOVA using factors for randomized group and shockable rhythm will be used rather than a two-sample t-test for the comparison of continuous and normally distributed variables. Continuous variables showing serious deviations from normality will be compared using a Van Elteren test. This test will also be used for the comparison of ordinal data.

For binary and categorical data, a Cochran-Mantel-Haenszel test will be used.

For primary and secondary variables, the effect of treatment will be estimated by an appropriate statistic and presented together with its associated 95% confidence interval.

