### 10.2.4 Neurocognitive Testing at Discharge

The total percentile scores of the Wechsler Memory Scale will be analysed using the same methodology as for the SF-36 questionnaire (see Section 10.2.3).

### 10.2.5 Neuron-Specific Enolase on Days 1 – 5

Enolase data collected on Days 1 to 5 will be analysed using a GEE2 (generalized estimating equations) model with identity link and normally distributed residuals. The model will include factors for shockable rhythm, randomised treatment, day and the interaction between treatment and day. An unstructured variance-covariance matrix will be used to account for interdependencies between the visits.

An overall Wald test of the interaction and the main effect of treatment will be used to assess whether there is any effect of treatment. The interaction will be tested using a Wald test to assess whether the shape of the evolution over the 5 days differs between the two groups.

In addition, treatment differences will be calculated and assessed at each day. To account for multiple testing, a stepwise Bonferroni correction will be used for both the calculation of the p-values and the confidence intervals. If the interaction is not statistically significant, an average treatment difference will be calculated by removing the interaction from the GEE model.

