### 10.2.6 ADL Scores at Discharge

ADL scores will be analysed using the same methodology as for the SF-36 questionnaire (see Section 10.2.3).

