### 10.2.7 6-Minute Walking Distance [m]

The 6-minute walking distance will be analysed using the same methodology as for the SF-36 questionnaire (see Section 10.2.3).

### 10.2.8 Creatinine and Urinary Output at Days 1 to 5

Creatinine and urinary output collected on Days 1 to 5 will be analysed using the same methodology as for neuron-specific enolase (see Section 10.2.5).

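### All survivor-average-effect intervals rest on 500 bootstrap samples, which leaves small but avoidable Monte Carlo error in their limits

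*SAP*

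**What the plan says.** SAP 10.2.3 takes the SACE as the effect measure for the SF-36 total score. It is computed "by weighing the result of each survivor by the estimated survival probability in the other group", with the survival probabilities taken from a logistic regression. On precision the section says: "The confidence interval will be obtained by bootstrapping (500 samples". That interval is the only inferential result specified there; the section names no test and no analytic standard error.

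The setting reaches further than SF-36 total:

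- SF-36 subscales (SAP 10.2.3): "In addition, the subscales will be analysed using the same methodology".
- Wechsler Memory Scale (SAP 10.2.4): the scores "will be analysed using the same methodology as for the SF-36 questionnaire (see Section 10.2.3".
- ADL (SAP 10.2.6) and 6-minute walking distance (SAP 10.2.7): the same cross-reference.

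SAP 10.2 calls for every secondary analysis in both the FAS and the PPS. One number therefore governs 4 × 2 = 8 intervals, plus those for the subscales.

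The confidence level comes from SAP 7.3, where for primary and secondary variables "the effect of treatment will be estimated by an appropriate statistic and presented together with its associated 95% confidence interval". SAP 7.7 leaves the secondary endpoints unadjusted for multiple testing. The SAP does not say whether the interval is percentile, normal-type or BCa, gives no seed, and does not say whether the survival model is refitted in each resample.

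**The concern.** A bootstrap interval carries two kinds of error: the sampling error of the trial, which the interval is meant to express, and Monte Carlo error from drawing a finite number of resamples. The second kind can be made as small as one likes at almost no cost.

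A few hundred resamples are generally enough to estimate a standard error, but a tail percentile is more demanding. Since 0.025 × 500 = 12.5, a lower 2.5% percentile limit depends on about the 12th or 13th most extreme resample.

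With no test beside it and no multiplicity adjustment, each SACE interval is likely to be read by whether it covers zero. For a result near the boundary that reading could turn on the seed. With seed and interval type both unstated, choices that can shift a borderline limit stay open until the analysis is run.

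**Working it through.** **Inputs.** Number of resamples B = 500 (SAP 10.2.3). Two-sided 95% level (SAP 7.3), so tail area 0.025, z = 1.96 and standard normal density φ(1.96) = 0.0584. The 500 is a chosen setting, so there is no derived figure in the plan to reproduce. Assumption: the bootstrap distribution is about normal. All results are in units of the SE of the estimated effect, so they need no outcome SD or survivor count.

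**1. Percentile limits.** The Monte Carlo SD of a limit is √(0.025 × 0.975 / B) / φ(1.96).
At B = 500: √(0.024375 / 500) = 0.00698, and 0.00698 / 0.0584 = 0.120 SE.
Relative to the half-width of 1.96 SE: 0.120 / 1.96 = 6.1%.

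**2. Normal-type limits** (estimate ± 1.96 × bootstrap SE). The Monte Carlo SD of a limit is 1.96 / √(2(B − 1)).
At B = 500: 1.96 / √998 = 0.062 SE, and 0.062 / 1.96 = 3.2%.

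**3. Where the seed can matter.** Let the true p be the two-sided p that an unlimited number of resamples would give for the same data. The seed can plausibly move the limit across zero when the observed effect lies within 1.96 Monte Carlo SDs of 1.96 SE.
Percentile, B = 500: 1.96 ± 1.96 × 0.1195 gives z from 1.726 to 2.194, or p from 0.084 down to 0.028.
Normal-type, B = 500: 1.96 ± 1.96 × 0.062 gives z from 1.838 to 2.082, or p from 0.066 down to 0.037.

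| B | Percentile SD (SE) | % of half-width | p band | Normal-type SD (SE) | % of half-width | p band |
|---|---|---|---|---|---|---|
| 500 | 0.120 | 6.1 | 0.028–0.084 | 0.062 | 3.2 | 0.037–0.066 |
| 5,000 | 0.038 | 1.9 | 0.042–0.059 | 0.020 | 1.0 | 0.046–0.055 |
| 10,000 | 0.027 | 1.4 | 0.044–0.056 | 0.014 | 0.7 | 0.047–0.053 |

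**4. Chance that two seeds disagree (percentile, B = 500).** The interval excludes zero if at most 12 resamples fall beyond it. With t equal to half the true p, q = P(Binomial(500, t) ≤ 12), and two seeds disagree with probability 2q(1 − q).

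- True p = 0.050: q = 0.518, disagreement 50%.
- True p = 0.036: q = 0.883, disagreement 2 × 0.883 × 0.117 = 21%.
- True p = 0.072: q = 0.089, disagreement 16%.
- True p = 0.028: 5%. True p = 0.089: 2%. True p = 0.016: 0.1%.

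Averaged over the results a trial could produce, disagreement is 1.6% per endpoint under no effect and 5.3% when the true effect equals 1.96 SE. At 10,000 samples these averages fall to 0.4% and 1.2%.

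**5. Check on the estimator itself.** The weighted SACE was simulated with assumed inputs: 112 randomised, 44, 62 or 73 survivors, three baseline covariates, outcome SD 20, and the survival model refitted in each resample. At B = 500 the seed-to-seed SD was 0.11–0.14 SE for percentile limits and 0.06 SE for normal-type limits. At B = 10,000 it was 0.025–0.032 and 0.014–0.015 SE. This agrees with steps 1 and 2.

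**The case against.** A reader might infer that borderline conclusions on SF-36, cognition, ADL and walking distance are not reproducible. The documents do not support that. A run with a recorded seed reproduces exactly at 500 samples, and a missing seed in the SAP does not mean that none will be recorded. What remains is Monte Carlo noise.

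A reader might also infer that 500 is too few whatever interval is used. The 0.12 SE figure assumes percentile limits, which the SAP does not name. For a normal-type interval the noise is half as large, and 500 resamples serve reasonably well.

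Further points on the other side stand. A shift of 3% to 6% of the half-width is small beside sampling error. These are unadjusted secondary endpoints, and no decision rule hangs on whether a SACE interval excludes zero, so a just-significant result would be weak evidence at any B. No number of resamples removes seed dependence exactly at the boundary: at true p = 0.050 two seeds still disagree about half the time with 10,000. Nor would more resamples help with a separate matter. The survival model draws on the covariate list of SAP 7.4, which includes post-baseline items such as enolase on days 1 to 5 and death within 7 days.

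None of this gives a reason to keep 500. It limits the weight of the point, not the value of the change.

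**Conclusion.** The point holds as a free improvement. Every SACE interval in the SAP carries avoidable Monte Carlo error because it is built from 500 resamples. The amount depends on an interval type that the SAP leaves open: about 0.12 SE per limit if percentile, about 0.06 SE if normal-type. The seed can alter whether zero is excluded only when the true p is about 0.03 to 0.08 in the first case, or 0.04 to 0.07 in the second. Outside those bands the reading is effectively settled.

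The consequence is confined to borderline results on secondary endpoints. The primary endpoint is analysed by multiple imputation and ANOVA (SAP 10.1) and does not use this bootstrap. The figures rest on an approximately normal bootstrap distribution; the simulation, with assumed survivor numbers and outcome SD, gave nearly the same values.

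**What to change.** In SAP 10.2.3, which 10.2.4, 10.2.6 and 10.2.7 inherit:

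1. Replace 500 by at least 5,000 bootstrap samples, preferably 10,000. The SD of a percentile limit falls from 0.12 to 0.04 SE (0.03 SE at 10,000).
2. Name the interval type.
3. State that the survival model is refitted in each resample.
4. Record a fixed seed.

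The cost is a sentence in the SAP and negligible computing time, since each resample needs only a small logistic fit on about 112 patients. There is no statistical downside.

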### 10.2.4 Neurocognitive Testing at Discharge

The total percentile scores of the Wechsler Memory Scale will be analysed using the same methodology as for the SF-36 questionnaire (see Section 10.2.3).

### 10.2.5 Neuron-Specific Enolase on Days 1 – 5

Enolase data collected on Days 1 to 5 will be analysed using a GEE2 (generalized estimating equations) model with identity link and normally distributed residuals. The model will include factors for shockable rhythm, randomised treatment, day and the interaction between treatment and day. An unstructured variance-covariance matrix will be used to account for interdependencies between the visits.

An overall Wald test of the interaction and the main effect of treatment will be used to assess whether there is any effect of treatment. The interaction will be tested using a Wald test to assess whether the shape of the evolution over the 5 days differs between the two groups.

In addition, treatment differences will be calculated and assessed at each day. To account for multiple testing, a stepwise Bonferroni correction will be used for both the calculation of the p-values and the confidence intervals. If the interaction is not statistically significant, an average treatment difference will be calculated by removing the interaction from the GEE model.

### 10.2.6 ADL Scores at Discharge

ADL scores will be analysed using the same methodology as for the SF-36 questionnaire (see Section 10.2.3).

### 10.2.7 6-Minute Walking Distance [m]

The 6-minute walking distance will be analysed using the same methodology as for the SF-36 questionnaire (see Section 10.2.3).

### 10.2.8 Creatinine and Urinary Output at Days 1 to 5

Creatinine and urinary output collected on Days 1 to 5 will be analysed using the same methodology as for neuron-specific enolase (see Section 10.2.5).

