4. INTRODUCTION

4.1. The clinical problem

There is absolutely no doubt that sudden cardiac death is a major problem in Belgium in terms of numbers of patients, medical impact and socio-economic impact. Each day, approximately 30 adults suffer from an unexpected out-of-hospital cardiac arrest in Belgium, a number exceeding the incidence of breast or prostate cancer with an estimated 25 new patients per day in Belgium. In addition, many cardiac arrest patients are young (mean age in our hospital 60±12 years, 56% of patients younger than 65 years) with a large economic potential for society. In the community, the occurrence of sudden death often takes center stage through highly mediatised cases of cardiac arrest in young sportsmen with or without a previously undiscovered cardiac anomaly. Apart from the traumatic experience of these dramatic sudden events, only 40% of patients that reach the hospital with spontaneous circulation survive without major neurological impairment or care dependency. An additional 5-10% of the cohort survives with major neurological impairment including a permanent vegetative state. These sobering outcome data and the large economic burden for society (estimated cost of a nursing home facility for these patients approximately 30-50000 €/year) mandate novel treatment strategies that could improve prognosis after cardiac arrest.

Apart from temperature management to avoid fever, no single in hospital randomized controlled intervention trial has improved outcome of these patients. In this way, there is absolutely no doubt that a positive result of the Neuroprotect post-CA trial would be a clear added value for this vulnerable and highly under-investigated patient group.

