#### 2.2.2 Secondary Efficacy Variables

% of patients with CPC 3-5 at discharge from ICU.

% of patients with CPC 3-5 at 180 days post-CA

SF-36 questionnaire at 180 days post-CA: total score and subscales

Neurocognitive testing at discharge from the hospital: total percentile scores of the Wechsler Memory Scale

Biomarkers – neuron-specific enolase on days 1 to 5.

Activities Daily Life (ADL) score at discharge from the hospital

6-minute walking distance (6MWD) [m] at discharge from the hospital

Renal function: creatinine [mg/dL] and urinary output [mL/24h] at days 1 to 5.

Length of ICU stay

Duration of mechanical ventilation

Placement of tracheostomy

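### Survivors too disabled to walk or be tested drop out of the planned survivor analysis of 6MWD and Wechsler, which can attenuate, and could reverse, an effect on severe disability

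*SAP*

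**What the plan says.** SAP 2.2.2 lists both endpoints at hospital discharge: "6-minute walking distance (6MWD) [m] at discharge from the hospital" and "Neurocognitive testing at discharge from the hospital: total percentile scores of the Wechsler Memory Scale". For the analysis, SAP 10.2.7 says "The 6-minute walking distance will be analysed using the same methodology as for the SF-36 questionnaire", and SAP 10.2.4 says "The total percentile scores of the Wechsler Memory Scale will be analysed using the same methodology as for the SF-36 questionnaire".

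The SF-36 method in SAP 10.2.3 is a SACE: the treatment effect among patients who would live whichever arm they were assigned. The problem it addresses is death, since "a considerable proportion of patients will have died prior to Day 180 and that therefore, the SF-36 results in these patients are not defined". The estimator works by "weighing the result of each survivor by the estimated survival probability in the other group". On the weights: "The estimated survival probabilities will be obtained from a logistic regression using survival as dependent variable".

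Multiple imputation (SAP 7.4) is specified for the primary endpoint only. Worst-case sensitivity analyses exist for missing day-180 CPC (10.2.2) and missing tracheostomy data (10.2.11). Nothing comparable exists for 6MWD or Wechsler, and neither document says what a living patient who cannot do the test is scored.

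**The concern.** A patient alive at hospital discharge but unable to stand or respond may have no 6MWD or Wechsler result. The survival weights cannot bring that patient back, because they multiply a result that does not exist, and the model behind them predicts being alive, not being testable. The missingness is caused by the disability that the endpoint is meant to measure.

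SAP 10.2.3 itself warns that comparing survivors alone is biased if survival depends on arm. The same reasoning applies to comparing testable survivors if testability depends on arm. Better neurological outcome is the trial's hypothesis (Protocol 4.3), so such a difference is plausible.

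At stake is the SAP's own estimand. If the strategy prevents severe disability in patients who would live either way, these two endpoints would understate the benefit. If it adds disability, they would hide the harm.

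**Working it through.** The documents give no expected mean, standard deviation or power for 6MWD or Wechsler, so there is no stated figure to reproduce. The 56 per group in Protocol 6.9.1 is for the MRI endpoint.

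**1. How many survivors could be affected.** Protocol 4.1 gives 40% surviving without major impairment, and adds: "An additional 5-10% of the cohort survives with major neurological impairment including a permanent vegetative state".
- Lower end: 5 / (40 + 5) = 11% of survivors. Per arm of 56: 56 × 0.05 = 2.8 of 56 × 0.45 = 25.2.
- Upper end: 10 / (40 + 10) = 20% of survivors. Per arm of 56: 56 × 0.10 = 5.6 of 56 × 0.50 = 28.

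That is about 3 to 6 of 25 to 28 survivors per arm with major impairment. Not all of them will be untestable.

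**2. Attenuation.** Let q be the untestable share of survivors in an arm and m the mean distance of those who can walk, equal in both arms. With inability counted as 0 m, the arm mean is m(1 − q) and the difference between arms is m(q₂ − q₁). Among the tested alone, the difference is m − m = 0.

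Assume that the same patients, 50% of the cohort, survive in either arm and that 5% v 10% of the cohort survive untestable. Then q is 0.05/0.50 = 10% v 0.10/0.50 = 20%.

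| Assumed m | Inability scored 0 m | Tested only |
|---|---|---|
| 200 m | 180 − 160 = 20 m | 0 |
| 300 m | 270 − 240 = 30 m | 0 |
| 400 m | 360 − 320 = 40 m | 0 |

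**3. Do the survival weights repair this?** The weighting was simulated with 56 per arm, 2,000 repetitions, one baseline covariate in a logistic survival model, walkers averaging 300 m and survival of 50% in both arms. Differences are the arm with more disabled survivors minus the other.
- Disabled survivors 5% v 10% of the cohort: −31.8 m when scored 0 m, −0.6 m when omitted. With 5,000 per arm: −28.9 m and +1.0 m.
- Disabled survivors 10% in both arms: −1.5 m and −0.8 m, so no material bias under either rule.

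In the first of these runs the standard deviation of the estimate across repetitions was about 42 m when scored 0 m and 32 m when omitted (both depend on the assumed spread of distances).

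**4. Reversal.** Suppose 40 patients survive under either arm and 35 of them walk 300 m in both. The other 5 walk 100 m under the intervention and cannot walk under control.
- Inability scored 0 m: (35 × 300 + 5 × 100)/40 − (35 × 300)/40 = 275 − 262.5 = +12.5 m.
- Tested only: 275 − 300 = −25 m.

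The patients who benefited enter one arm's average as slow walkers and are absent from the other. The same logic holds for Wechsler with the lowest percentile in place of 0 m; no document figure allows its size to be given.

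**The case against.** Several stronger readings are tempting, and the documents do not support them.

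- **Deaths turned into disabled survivors.** A reader might infer that the plan hides this. It does not: SACE targets patients who would live under either arm, so rescued patients lie outside it by definition. Scoring 0 m can even mislead here. Per 100 patients, let control have 40 walkers at 300 m and 5 disabled, and the intervention the same 45 plus 5 rescued but disabled. The true SACE is 0, and omission gives 0. Scoring 0 m gives 300 × 40/50 − 300 × 40/45 = 240.0 − 266.7 = −26.7 m before weighting. Weights correct this only as far as baseline covariates identify the rescued: a simulation with survival of 45% v 50% gave −24.6 m scored 0 m and +1.3 m omitted. This stands as a limit on the fix.
- **11-20% of survivors untestable.** Protocol 4.1 describes major impairment, not inability to walk or be tested. Nor are 11% and 20% a contrast between arms; they are two ends of one cohort estimate.
- **The SAP prescribes omission.** It is silent. Omission is what the weighting rule yields when there is no result. If sites record 0 m for patients who cannot walk, the 6MWD part falls away, but no such rule is written.
- **Severe disability goes unseen.** CPC 3-5 at ICU discharge and at day 180 captures it, with death counted as CPC 5. ADL measures dependence, and nothing says that it requires the patient to perform a test. SAP 7.2 and 8.1 would also show unequal numbers tested and discharged.

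What remains is the effect on disability among patients who survive under either arm. None of these objections removes it.

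**Conclusion.** The point holds for 6MWD and Wechsler. The SACE rule as written handles death but not survival with inability to be tested, so it misestimates the SAP's own estimand whenever treatment changes severe disability among patients who would live either way. The usual result is attenuation: 30 m shown as 0 at 10% v 20% untestable and a 300 m mean, or 20-40 m lost for means of 200-400 m. Reversal is possible when patients spared inability walk only short distances.

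The walking distances and the imbalance between arms are assumptions; the documents supply neither. With equal untestable shares there is no bias. In the simulation at this sample size, the shift is smaller than the sampling standard deviation of the estimate. The endpoints are secondary, with no multiplicity adjustment across them (SAP 7.7), and the primary analysis and sample size are unaffected. This is a cheap improvement rather than a flaw that threatens the trial's main conclusion.

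**What to change.** Before unblinding, add to SAP 10.2.4 and 10.2.7:

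- Survivors unable to perform the test because of neurological or physical disability are scored 0 m (6MWD) or the lowest percentile (Wechsler) and enter the SACE analysis with that value.
- Tests missed for unrelated reasons stay missing. The two are separated, blind to arm, using CPC at hospital discharge (already scheduled in Protocol 6.8.1) together with source notes. CPC alone does not establish walking ability.
- The number untestable is reported by arm.
- The tested-only analysis is kept as a sensitivity analysis, since the two rules can diverge when survival differs between arms.

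ADL needs no preset score.

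The cost is a few sentences of SAP text and, because all patients were already included by the blinded review of 5 March 2018 (SAP 4.2), some retrospective review of why tests were not done. The statistical price is a spike at the lowest score, a wider interval, and more reliance on how well the survival model identifies patients who would live under either arm.
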